7.2.5 Safety analyses

Standard BI summary tables and listings will be produced. All adverse events with an onset between informed consent signature and end of the post-TARA IDI will be assigned to the study period for evaluation.

All study participants will be included in the safety analysis. In general, safety analyses will be descriptive in nature and will be based on BI standards. No hypothesis testing is planned. Frequency, severity, and causal relationship of adverse events will be tabulated by system organ class and preferred term after coding according to the current version of the Medical Dictionary for Drug Regulatory Activities (MedDRA) at database lock.

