8.6 STUDY MILESTONES

The **start of the study** is defined as the date when the first participant in the whole study signs e-informed consent.

The end of the study is defined as the date of the last visit of the last participant in the whole study ("Last Participant Completed"). Early termination of the study is defined as the premature termination of the study due to any reason before the end of the study as specified in this protocol.

Temporary halt of the study is defined as any unplanned interruption of the study by the sponsor with the intention to resume it.

Suspension of the study is defined as an interruption of the study based on a Health Authority (HA) request.

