#### 4. CHANGES IN THE PLANNED ANALYSIS OF THE STUDY

As a result of the limited sample size (5 instead of the planned 50 individuals with chronic obstructive pulmonary disease (IwCOPD), the pre-planned analyses for this study will not be conducted. Instead, listings of participants' data will be generated for inclusion in an abbreviated study report. The primary and secondary assessments will be listed for each participant, and from the further assessments, only the engagement with TARA will be listed. No subgroup analyses will be performed.

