## 6. GENERAL ANALYSIS DEFINITIONS

#### 6.1 TREATMENT(S)

Treatment specification is not applicable as there are no pharmacological treatments assigned nor administered as part of the study. Analyses will be performed separately by cohort, as different versions of TARA were used.

The following study periods will be defined with respect to safety analyses:

• Post-Informed-Consent: after informed consent

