#### 7.8 SAFETY ANALYSIS

Safety analysis will be performed as defined in the CSP. All safety analyses will be performed on the ES.

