#### 7.8.1 Adverse Events

Unless otherwise specified, the analyses of AEs will be descriptive in nature. All analyses of AEs will be based on the number of subjects with AEs and NOT on the number of AEs.

The analysis of AEs will be based on the concept of treatment emergent AEs. That means that all AEs that occurred after signing the informed consent until the end of study (Week 12) will be assigned to the treatment observed at baseline (background treatment). Non-treatment-emergent AEs will be assigned to "screening" or "follow-up" (after Week 12).

According to ICH E3 (4), in addition to Deaths and serious adverse events, 'other significant' AEs need to be listed in the clinical study report. These will be any non-serious adverse event that led to an action taken with study drug (e.g. discontinuation or dose reduced or interrupted). An overall summary of adverse events will be presented.

The frequency of subjects with AEs will be summarized by treatment, primary system organ class and PT. Separate tables will be provided for subjects with serious adverse events (SAEs), AEs leading to treatment discontinuation, AEs of at least moderate severity and related AEs.

The system organ classes (SOCs) will be sorted by default alphabetically, PTs will be sorted by frequency (within SOC).

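### SAP 7.8.1 closes the treatment-emergent AE window at Week 12, short of the protocol's AE study period, and SAP section 4 does not declare the change

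*SAP*

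**What the plan says.** SAP 7.8.1 bases the AE analysis on treatment-emergent AEs. The window opens at consent, and AEs from then "until the end of study (Week 12) will be assigned to the treatment observed at baseline", meaning the participant's background inhaled medication. For the remainder, "Non-treatment-emergent AEs will be assigned to" one of two labels: *screening*, or *follow-up* for AEs after Week 12. SAP 6.7 sets Week 12 at the administration of Survey 5. The tables are then planned as follows: "The frequency of subjects with AEs will be summarized by treatment, primary system organ class and PT".

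The protocol sets a longer period. Its section 7.2.5 reads: "All adverse events with an onset between informed consent signature and end of the post-TARA IDI will be assigned to the study period".

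Two other places in the SAP bear on this. SAP 7.8, which introduces 7.8.1, states: "Safety analysis will be performed as defined in the CSP". SAP 6.1 lists the study periods for safety and gives only one: "Post-Informed-Consent: after informed consent". SAP section 4, which records the changes to the planned analysis, attributes the move to listings to the "limited sample size (5 instead of the planned 50 individuals" and says nothing about the AE period.

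**The concern.** The protocol and SAP 7.8.1 set different ends for the period in which AEs are evaluated, and SAP 7.8 says there is no difference. A programmer working from SAP 6.1, SAP 7.8 and the protocol would treat an AE that starts after Survey 5 like any other. A programmer working from 7.8.1 would class it as non-treatment-emergent.

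This affects AE collection that the protocol plans. Under Protocol 6.2.3 the follow-up visit comes after Survey 5, and the site should ask about AEs there. Survey 6 comes after that visit, and a subset of participants is also interviewed. Interviews are monitored for AEs (Protocol 10.3) and are a named source of AE reports (Protocol 5.3.7.1). At stake is whether AEs that start in this interval appear in the summary tables by background treatment or only under a separate label.

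**Working it through.** No figure in the plan needs reproducing. The check compares the texts and then bounds the length of the gap.

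**1. The texts side by side**

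| Source | Start | End |
|---|---|---|
| Protocol 7.2.5 | Consent | End of the post-TARA interview |
| SAP 7.8.1 with SAP 6.7 | Consent | Week 12, i.e. administration of Survey 5 |
| SAP 6.1 | Consent | None stated; a single period |
| SAP 7.8 | As protocol | As protocol |
| SAP section 4 | No change declared | No change declared |

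**2. Does the move to listings make the point moot?** No. SAP section 7 applies its listings rule to the primary, secondary and further assessments, demographics and baseline characteristics; it does not name safety. SAP 7.8.1 still plans an overall AE summary and frequency tables. It adds separate tables for serious AEs, AEs leading to discontinuation, AEs of at least moderate severity, and related AEs.

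**3. Is there a reason in the text for stopping at Survey 5?** The obvious one would be to isolate AEs during TARA use. That does not fit, because the window opens at consent and so already takes in screening and the run-in, both before TARA. The treatment to which AEs are assigned is the background medication, and no text stops that at Survey 5. The *screening* label is also empty, since both the window and AE reporting (Protocol 5.3.7.2) begin at consent.

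**4. Length of the gap.** Inputs:
- maximum observation from consent to interview: 16 weeks (Protocol synopsis, duration of observation)
- run-in: 2 weeks (Protocol 6.2.1)
- TARA period, with Survey 5 at its end: 12 weeks (Protocol 6.2.2)

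Gap = observation − run-in − TARA period − (screening + tracker shipment).

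16 × 7 = 112 days; 112 − 14 − 84 = 14 days if screening and shipment take no time. The documents do not give that time, so these values are assumed:

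| Screening + shipment (assumed) | Gap from Survey 5 to interview |
|---|---|
| 0 days | 14 days |
| 3 days | 11 days |
| 7 days | 7 days |
| 14 days | 0 days |

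The follow-up visit, which applies to every participant and not only to those interviewed, is due within 7 days of the site's notification (Protocol 6.2.3).

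**5. Effect on a table.** SAP 7.8.1 counts subjects, not events. A participant leaves a cell only if every AE that person has in that cell starts after Survey 5. One person moving changes a cell by 1 of 5 = 20% of the sample.

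**The case against.** The strongest reply is that the SAP's phrase follows the protocol's own usage. Protocol 3.1 describes a 12-week study duration and collects its end-of-study measures at 12 weeks. The flow chart shows a 12-week study period followed by post-study activities. This stands as far as the phrase goes. For the same reason, one reading should not be drawn: a reader might infer that SAP 7.8.1 misdefines the end of the study, because Protocol 8.6 says "The end of the study is defined as the date of the last visit of the last participant in the whole study". That is a trial-level milestone and was never a cut-off for an individual's AEs. The relevant comparison is with Protocol 7.2.5, which sets the AE period specifically and runs it to the interview.

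Second, Protocol 7.2.5 does not use the term treatment-emergent, and a SAP may refine what the protocol evaluates. A split at the end of the TARA period is a possible choice. But SAP 7.8 claims to follow the protocol, section 4 is silent, and the split as written does not isolate TARA use.

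Third, SAP 6.1 gives a start and no stop, so alone it is less specific than 7.8.1 and not plainly opposed to it. That is fair. Still, it lists the safety periods and includes no follow-up period.

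Fourth, SAP 7.8.1 does not say in terms that follow-up AEs are left out of the tables. That is an inference: the analysis rests on treatment-emergent AEs, the tables are by treatment, and follow-up AEs are assigned to no treatment. The requirement to list deaths, serious AEs and other significant AEs carries no Week 12 limit.

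**Conclusion.** The inconsistency is real and undeclared, and its severity is minor. As written, AEs that start after Survey 5 would be non-treatment-emergent and fall outside the tables by background treatment, although the protocol assigns them to the study period.

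The gap is at most about 14 days, assuming Survey 5 is administered at 12 weeks and the 16-week maximum holds. Screening, shipment or a late survey shortens it, possibly to nothing. Any table cell changes by at most 1 of 5 participants, assuming no more than one person's AEs in that cell all fall in the gap. Nothing in the documents shows that such an AE occurred. Safety is descriptive, with no hypothesis testing.

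Two stronger conclusions are tempting, and the documents do not support them:
- That AEs are lost. They are collected and reported to the end of the study (Protocol 5.3.7.2) and relabelled, not discarded.
- That a participant who does not complete Survey 5 has no cut-off. SAP 6.7 refers to the administration of the survey, not its completion, and Protocol 6.2.2 sends it at 12 weeks. Such a participant can still have a Week 12 date.

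**What to change.** In SAP 7.8.1, end the window at the end of the post-TARA interview, or at the participant's last study contact if there is no interview. The second rule is an addition: Protocol 7.2.5 names only the interview, which covers a subset. For participants not selected for interview, Protocol 6.2.3 ends participation at Survey 6. Remove the assignment to *screening* and *follow-up*, so that 7.8.1 agrees with SAP 6.1. Add AE onset day relative to Survey 5 to the AE listing.

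The cost is one or two sentences and one listing column, with no new data. The downside is that AEs after the TARA period are pooled with earlier ones in the tables; the onset-day column keeps them identifiable. If the Week 12 split is intended, the alternative is to keep it and declare it, with its reason, in SAP section 4.

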7.2 PLANNED ANALYSES

7.2.1 General considerations

In order to conclude that engagement with TARA leads to a patient benefit with regards to changes in breathlessness, it is important to confirm that any reduction in breathlessness at follow-up compared to baseline is not a consequence of a reduction in physical activity. Therefore, a preliminary analysis will be conducted to evaluate if changes in breathlessness vary with changes in physical activity from baseline to follow-up.

Analysis will be performed separately for each cohort (Cohort 1: non-pharmacological self-management support; Cohort 2: non-pharmacological + pharmacological self-management support). Pooled analysis between the cohorts will not be performed.

All patients enrolled will be included in analysis. Additional explorative analysis will be described in statistical analysis plan.

Preliminary Analysis:

Study participants will be divided into three categories based on the level of change in their physical activity from baseline to 12-week follow-up using steps as a standard measure of activity. Each participant's activity (steps) data will be descriptively analysed and standardized. Based on the distribution of observed data, participants will then be categorized into groups using an appropriate criterion of change such as:

- Decreased activity: Activity level has decreased 1 SD or more at follow-up
- Increased activity: Activity level has increased 1 SD or more at follow-up
- No change: All other participants

Following this categorization, differences in breathlessness scores (using the CRQ-SAI dyspnea domain) will be computed for each group between baseline and 12-week follow up

16 Sep 2021

Page 47 of 93

Proprietary confidential information © 2021 Boehringer Ingelheim International GmbH or one or more of its affiliated companies

and comparisons conducted between groups. This analysis will evaluate if changes in breathlessness continue to be seen regardless of changes in physical activity.

[figure not shown]

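### SAP 7.8.1 groups adverse events by the unassigned background inhaler without naming cohort, and its 'study drug' and discontinuation rules are not defined for TARA

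*SAP*

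**What the plan says.** SAP 7.8.1 assigns each AE that occurs after consent and up to Week 12 to a treatment: such AEs "will be assigned to the treatment observed at baseline (background treatment"). It then states: "The frequency of subjects with AEs will be summarized by treatment, primary system organ class and PT". Further tables cover serious AEs, AEs that led to discontinuing treatment, AEs of moderate or worse severity, and related AEs, together with an overall summary. Besides deaths and serious AEs, the report must list other significant AEs, defined as "any non-serious adverse event that led to an action taken with study drug".

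SAP 6.1 says: "Treatment specification is not applicable as there are no pharmacological treatments assigned nor administered as part of the study". It continues: "Analyses will be performed separately by cohort, as different versions of TARA were used". SAP 7.8 opens with "Safety analysis will be performed as defined in the CSP".

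Protocol 7.2.1 says of the two cohorts: "Pooled analysis between the cohorts will not be performed". Protocol 7.2.5 says: "Frequency, severity, and causal relationship of adverse events will be tabulated by system organ class and preferred term". It names no split by inhaler and plans no hypothesis test. Protocol 4.1 states that no investigational medicinal product is given, and the synopsis lists TARA version 3 as the test product. Protocol 3.3.2 requires a prescription for one of two inhalers, Spiriva Respimat or Stiolto Respimat.

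**The concern.** The intervention is TARA. Protocol 1.3 gives Cohort 1 version 3.1 and Cohort 2 version 3.2, which adds the medication-support component, and the cohorts exist so that this addition can be looked at. AE tables would therefore be expected to show events per TARA version. SAP 7.8.1 names a different variable, one that the study neither assigns nor controls. A programmer working from that section alone would build columns for inhalers, and a Cohort 1 and a Cohort 2 participant on the same inhaler would share a column.

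The second part concerns events that end use of the intervention. Protocol 1.4.2 notes that participants may disengage from TARA or the study at any time, so a participant could stop TARA because of an AE. If the reporting rules recognise only actions on a drug, such an event would appear as an ordinary AE and nothing would show that it ended TARA use.

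**Working it through.** There is no figure in the plan to reproduce, so this is a comparison of texts with some counting.

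**Step 1. Which variable groups the AEs?**

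| Place | Grouping |
|---|---|
| SAP 6.1 | Cohort; treatment not applicable |
| SAP 7.8 | As in the protocol |
| Protocol 7.2.1 | Each cohort separately, no pooling |
| Protocol 7.2.5 | System organ class and preferred term; no inhaler split |
| SAP 7.8.1 | Background treatment at baseline; cohort not named |

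SAP 7.8.1 is alone in using the inhaler. SAP 4, which sets out changes to the planned analysis, does not declare it.

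**Step 2. What would the columns be?** Inputs: 2 cohorts (protocol 3.1) and 2 eligible inhalers (protocol 3.3.2).
- 7.8.1 read alone: up to 2 columns, one per inhaler, each able to contain both TARA versions.
- 7.8.1 read together with 6.1: up to 2 × 2 = 4 columns for 5 participants.
- By cohort only: up to 2 columns, one per TARA version.

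The text does not say which of these applies.

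**Step 3. Would an AE that ended TARA use be picked out?** Take a non-serious AE after which the participant stops using TARA and keeps the inhaler unchanged.
- Other significant AEs: the rule needs an action on a study drug. None was taken, so the rule is not met.
- Table of AEs that led to discontinuing treatment: the only treatment 7.8.1 identifies is the background inhaler, whereas the protocol's test product is TARA. The result depends on which meaning is taken.
- Elsewhere the SAP ties use to TARA: 7.3 replaces compliance with engagement, and 7.7 measures exposure as days between first and last login. So exposure refers to TARA while AEs are assigned to an inhaler.

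**Step 4. Are the AE tables still planned?** SAP 4 replaces the pre-planned analyses with listings because 5 rather than 50 participants were available. The data it names for listing are the primary and secondary assessments and TARA engagement. AEs are not named, and 7.8.1 still describes a summary and frequency tables, so the grouping rule still matters.

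**Step 5. Size.** One participant is 1/5 = 20% of the total. The documents do not give the split of the 5 by cohort or by inhaler. If a column holds *k* of the 5, one participant is 1/*k* of it:

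| *k* (assumed) | 1 | 2 | 3 | 4 | 5 |
|---|---|---|---|---|---|
| One participant | 100% | 50% | 33% | 25% | 20% |

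For example, one participant with an AE in a column of 2 rather than 3 changes the frequency by 50% − 33% = 17 percentage points. A column with no AEs stays at 0% whatever its size.

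**The case against.** The strongest reply is that the texts can be read together. SAP 6.1 makes no exception for safety, and its next statement defines the study period for safety analyses, so the by-cohort rule plainly extends to AEs. Protocol 7.2.1 bars pooling, and SAP 7.8 defers to the protocol. On that reading the tables show inhaler within cohort and nothing is combined. This stands: a reader might infer that the SAP prescribes pooling of the TARA versions, but no sentence says so. What remains is that 7.8.1 does not name cohort and the user must choose between readings.

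A second reply is that the inhaler belongs in the safety section. The protocol defines AEs and adverse reactions against a medicinal product (5.3.6), sets drug-based causality criteria, and speaks of the inhaler as a studied drug (5.3.7). That justifies showing the inhaler alongside each event. It does not make the inhaler the table grouping, which protocol 7.2.5 does not do. A reader might also infer a planned comparison of two marketed drugs. None is planned: the analysis is descriptive, although side-by-side columns could invite one.

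Third, it is tempting to say that AEs ending TARA use are lost. They are not. All AEs are reported regardless of causality (protocol 5.3.7.2) and would enter the frequency tables. The words study drug occur only in the rule for other significant AEs, so failure of the discontinuation table is possible, not established.

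Finally, 5 participants in sequential, non-randomised cohorts could not show whether version 3.2 carries more risk, however the tables are arranged. That is correct and limits the consequence.

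**Conclusion.** The point holds as an inconsistency in the SAP that should be corrected. SAP 7.8.1 uses the unassigned inhaler as its only stated grouping and omits cohort, against SAP 6.1 and protocol 7.2.1 and 7.2.5. Taken alone it would mix the TARA versions; taken with 6.1 it need not. The rule for other significant AEs does not cover a non-serious event that ended TARA use, and the discontinuation table may not.

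Every AE table in 7.8.1 is affected, in descriptive presentation only. No test, estimate or efficacy result changes. Beyond 20% of the total per participant, no shift in any frequency can be stated, because the cohort and inhaler splits are not given. Mixing of versions within a column also assumes that both cohorts are represented among the 5. SAP 6.1 implies this by saying that different versions were used, but gives no counts.

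**What to change.** In SAP 7.8.1:

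1. Make cohort (TARA version 3.1 or 3.2) the grouping for all AE tables, in place of background treatment.
2. Show background treatment as a column in the AE listing, or at most as a split within cohort. Either satisfies SAP 6.1 and protocol 7.2.1.
3. Define action taken and leading to discontinuation, for reporting purposes, so that they include stopping or interrupting TARA or the study. Report actions on the inhaler separately.
4. Say in SAP 4 whether the AE tables are kept or replaced by listings.

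The cost is a few lines of SAP text and one changed grouping variable. Cohort is entered in the study database at the first data transfer (SAP 8) and is already a column in the participant listings (SAP 7). The one open item is whether the AE form or the TARA login record shows that an event led to stopping TARA; the visible text does not settle this and it should be checked before the definition is finalised.

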1.4.1 Benefits

Potential benefits of the fully developed TARA DBCI include improving knowledge of COPD and its treatments and how treatment can improve symptoms and outcomes, verifying inhaler technique, and learning new skills that may improve self-management of COPD; these same potential benefits are applicable to study participants engaging with the TARA DBCI working prototype (version 3).

1.4.2 **Risks**

No adverse effects have been identified during the user experience testing rounds of components of the intervention or in the first clinical study (CRT1; 352.2133).

Study 352.2154 will be the second study that IwCOPD will engage with TARA in a real-world setting. There is a potential for (disease-related) behaviour change and consequent risks associated with changes in behaviour; in light of the fact that (i) study participants will only be allowed to log-on to TARA after recommendation by their primary physician, (ii) the

16 Sep 2021

Page 20 of 93

Proprietary confidential information © 2021 Boehringer Ingelheim International GmbH or one or more of its affiliated companies

medical oversight of the participant is by their primary physician and (iii) no therapeutic recommendations are being provided by the software, risks associated with engagement with TARA in this study are considered low. The time required to engage with TARA is a potential inconvenience and is mitigated by the option for study participants to disengage from TARA / study at any time.

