4. TREATMENTS

4.1 INVESTIGATIONAL INTERVENTION

No IMP treatments will be administered in this study.

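### SAP 7.8.1 ties its special adverse-event outputs to an undefined study drug and to background treatment, so events that end TARA use or study participation are not flagged as such

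*SAP*

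**What the plan says.** SAP 7.8.1 sets up two outputs meant to pick out AEs with consequences.

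- **Other significant AEs**, listed in addition to deaths and serious events: "These will be any non-serious adverse event that led to an action taken with study drug". The examples are "e.g. discontinuation or dose reduced or interrupted".
- **Separate tables**, one of which covers "AEs leading to treatment discontinuation".

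The SAP does not define study drug. The nearest it comes to defining treatment for the AE analysis is in the same section, where events after consent and up to Week 12 "will be assigned to the treatment observed at baseline (background treatment").

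Elsewhere the documents say there is nothing of that kind to act on. Protocol 4.1: "No IMP treatments will be administered in this study". SAP 6.1: "there are no pharmacological treatments assigned nor administered as part of the study". SAP 7.3 repeats this when it sets compliance aside in favour of engagement with TARA. The protocol synopsis names TARA as the test product, and SAP 7.7 measures exposure from first to last TARA log-in.

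**The concern.** For a digital self-management tool, an AE that makes a user stop the tool or leave the study is direct information on tolerability. The protocol recognises the route by which harm could arise: "There is a potential for (disease-related) behaviour change and consequent risks associated with changes in behaviour" (Protocol 1.4.2). The same section notes that participants may disengage from TARA or from the study whenever they wish.

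The two outputs in SAP 7.8.1 that should bring such events to the surface depend on dosing actions with a drug, or on stopping a treatment that the section equates with the inhaler. A report with nothing in either output could be taken to show that no AE led anyone to stop TARA, when neither output was clearly tied to TARA. The study exists to judge whether TARA merits larger randomised testing (Protocol 1.3), so that misreading would concern the product under test.

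**Working it through.** No arithmetic applies. The check is to ask what study drug and treatment could refer to, and then to follow one event through the planned outputs.

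**Possible referents**

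1. *Nothing.* Protocol 4.1, SAP 6.1 and SAP 7.3 say that no such product or treatment is administered, and the SAP passages add that none is assigned. On this reading the other significant category is empty whatever happens.
2. *The background inhaler.* SAP 7.8.1 assigns AEs to background treatment. In its pregnancy and reporting text, Protocol 5.3.7.1 refers to Spiriva or Stiolto Respimat as study medication and speaks of a studied drug of the sponsor's. On this reading both outputs follow changes to a prescribed marketed product.
3. *TARA.* The synopsis lists it as the test product, the header of the amendment form in Protocol 11.1 enters it in the investigational product field, and Protocol 1.3 describes a digital behavioural treatment. On this reading, stopping TARA could qualify. But the dose-reduction example has no meaning for TARA, and SAP 7.8.1 itself attaches the word treatment to the inhaler.

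The documents do not choose between these. Within SAP 7.8.1 the text favours the second.

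**One event followed through**

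Take a non-serious SARS-CoV-2 infection, with the inhaler continued unchanged. Protocol 3.3.4.2 requires that the participant be discontinued from the study.

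| Output | Does the event appear? |
|---|---|
| Reporting to investigator and sponsor (Protocol 5.3.7.1, 5.3.7.2) | Yes, regardless of causality |
| Overall summary and frequency by organ class and preferred term (Protocol 7.2.5, SAP 7.8.1) | Yes, if the participant is in the entered set |
| Table of AEs of at least moderate severity | Only if graded so |
| Table of related AEs | Only if judged related; Protocol 5.3.7.1 frames that judgement around a medicinal product |
| Other significant AEs | No under referents 1 and 2, as no action was taken with a drug; unclear under 3 |
| AEs leading to treatment discontinuation | No if treatment is the background inhaler; otherwise unclear |
| Any other output linking the event to leaving the study | None found |

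SAP 7.8 defers to the protocol for the safety analysis, but this does not fill the last row. Protocol 7.2.5 specifies frequency, severity and causal relationship, and does not mention discontinuation.

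The same trace applies to a non-serious AE that leads a participant to stop TARA by choice. It is counted as an AE, and nothing specified in the plan marks it as the reason for stopping.

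**The case against.** The strongest reply is that little is lost. AEs from all sources, including the website, the interviews and the TARA platform, go to the investigator and the sponsor whatever their cause. Protocol 7.2.5 promises the sponsor's standard tables and listings, and SAP 7.8.1 adds an overall summary, organ-class frequencies and the tables "AEs leading to treatment discontinuation, AEs of at least moderate severity and related AEs". SAP 4 states that only 5 of the planned 50 participants are available and that engagement with TARA is listed, so a reader of the report could set each person's AEs beside their TARA use. **This stands, and it limits the point to a missing flag.**

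Three stronger readings are tempting, and the documents do not support them.

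- *That these AEs go unrecorded or drop out of the report.* They are collected and tabulated. Only their identification as leading to discontinuation is absent.
- *That the study drug does not exist, so the outputs must be empty by construction.* The term has conflicting referents rather than none, and the discontinuation table refers to treatment, not to study drug.
- *That a rate of hidden AE-driven stops can be calculated.* The documents give no count of such events, so any rate would be hypothetical.

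A further objection concerns the remedy. Participants may use TARA as much or as little as they like (Protocol 3.1 and 6.2.2), so a pause has no threshold and log-in gaps cannot show that an AE caused it. Participants may also withdraw without giving a reason (Protocol 3.3.4.1). Both points are fair. They argue for a rule based on the reported reason, with missing reasons shown.

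The reply does not remove the defect in the rule. Placing AEs beside log-in dates shows timing, not the reason for stopping, and a stated rule that selects the wrong events is more than an omitted detail.

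**Conclusion.** The point holds in limited form. SAP 7.8.1 keys other significant AEs to an undefined study drug, and the discontinuation table to a treatment that the section equates with the background inhaler. The study administers no investigational medicinal product, and TARA is the product under test. A non-serious AE that ends TARA use or study participation, including the discontinuation required by Protocol 3.3.4.2, would be reported as an AE but not flagged as leading to discontinuation. An empty output under either heading could therefore be misread as tolerability of TARA.

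With 5 participants the practical effect is minor. No size can be given beyond that, because the documents do not say whether any such event occurred.

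The conclusion assumes that treatment in the discontinuation table has the meaning used earlier in SAP 7.8.1. If the sponsor meant TARA, the table would work for TARA stops, but the text would still need to say so and to cover leaving the study. The AE form is not in the documents, so it cannot be checked whether the form already records action taken with TARA.

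**What to change.** In SAP 7.8.1, replace the study-drug rule with wording such as:

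> *Any non-serious AE reported as the reason for stopping or interrupting TARA, or for withdrawal or discontinuation from the study, whether by the participant or under the protocol.*

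Then:

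- use the same reasons to define the AE discontinuation table, so that the two outputs agree;
- show any change in background inhaler in a separate listing column, apart from stopping TARA or leaving the study;
- show reason not given where a participant stopped or withdrew and no reason is recorded, so that a blank is not read as absence of an AE.

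The phrase covering discontinuation under the protocol is needed so that the SARS-CoV-2 rule in Protocol 3.3.4.2 is included. Basing the rule on the reported reason avoids having to set a log-in gap that counts as stopping.

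The cost is a wording change, one or two listing columns, and a review of the AE and site records of about five participants. If those records do not hold the reason, the entry is reason not given. The change concerns reporting only and alters no clinical procedure.
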